4.3 Exclusion criteria

Exclusion criteria at *participant/girl* level:

- 1) Following and/or participating in an another individual or group-based mindfulness-based training in academic year 2025/2026 or 2026/2027.

Exclusion criteria at the *school* level (to mitigate any risk of difficulties in trial implementation):

- 1) Not having a headteacher in academic year 2025/2026 or 2026/2027.
- 2) Judged as 'inadequate' during the most recent school inspection by the Dutch Inspectorate of Education.
- 3) Implementing another mindfulness-based intervention in academic year 2025/2026 or 2026/2027.

4.4 Sample size calculation

Multi-level models are used with individuals nested in dyads. To determine the required sample size for this cRCT study power analyses were conducted using Optimal Design Plus – Evidence (Raudenbusch, 2011). These analyses were based on an alpha level (α) of .05, with three measurement points (baseline and two follow-up measurements), and an intraclass correlation (ICC) of .40 between two friends (ρ). This ICC was derived from observed ICCs for perceived support within friendship dyads ($n = 266$ pairs) in an existing dataset of adolescents with an average age of 13. For average risk girls (M), the multilevel power analysis was based on an expected effect size (Cohen's d) of 0.50, indicating a small to medium effect. The power analysis showed that, to achieve a power level of 0.80, at least 122 average-risk friendship dyads would need to be included. However, we will aim to oversample to a maximum of 160 dyads in order to be able to compensate for loss to follow up .

5. TREATMENT OF SUBJECTS

5.1 Investigational product/treatment

Girls United blended mindfulness program

The Girls United prevention program aims to foster social-emotional-behavioral self-regulation within a supportive close-friendship context through incorporation of both dyadic and individual experiential learning. Developed between 2020 and 2023 using the Intervention Mapping Approach for health promotion planning (Vuijk & Bierhaus, 2023a; 2023b; 2023c; 2023d; Vuijk & Norrgren, 2024) the program includes 14 weekly online lessons delivered by trained facilitators. The training sessions will be recorded with BigBlueButton for training and intervision purposes but only when the parents/main caretakers provided their approval on the informed consent form. The dyads will receive links via email for entering the BigBlueButton meeting rooms. The lessons integrate psychoeducation and mindfulness practices, guiding participants in using the application *App yourself Happy* app (Vuijk et al., 2023) within their friendship dyads. In order to teach and stimulate girls to discover new healthy and positive shared alternatives for excessive co-rumination and rumination (getting out of autopilot negative reactivity), to stimulate present-moment awareness and appreciation of pleasant shared experiences and interactions, to encourage girls to share their interpersonal responses to pleasant experiences and positive affect with each other, to teach girls to work skillfully with difficult emotions during activities and interactions and to support friendship dyads to incorporate these healthy alternatives in their daily lives, dyadic-friendship girls will participate and will be supported together by the training program and encouraged to use the App yourself Happy module 'Healthy, joyful dyadic activities' on a daily basis. This module contains 150 healthy and joyful behavioral activation activities for dyadic use with the following categories: Beauty, On the road, Creative, Educative, Game time, Indoor, Outdoor, Mindfulness, Sport, Relax, and Kitchen. Each activity is presented on a photocard with fun and inspiring tips about the preparation of the activity and information about the costs and other important aspects (e.g., 'for this activity you need a towel'). Girls will be able to select five activities and share these with their dyad-friend via a WhatsApp message.

Friendship dyads will be encouraged in the weekly training sessions to do at least one or two activities each week. These behavioral activities (including the preparations and the reflections on the activities through journaling and reflections during the weekly training sessions) will function as a natural backbone to train several mindfulness-skills: being in the present moment (present-moment awareness), conducting random acts of kindness, experiencing joy and gratitude using the ten fingers gratitude practice, using the pleasant experiences calendar and creating more nurturing experiences, and using the unpleasant experiences calendar and diminishing the impact of depleting experiences. In every training

session, a new mindfulness practice will be introduced by connecting practice with upcoming activities and skills practicing. The use of these practices will be stimulated by several animation videos with explanations about co-rumination, brain functioning on automatic pilot and a guided mediation practice. Working with mindfulness skills and practices during the activities and within daily live interactions will be evaluated and reflected on during the online training sessions, and girls will be encouraged and trained to incorporate these mindfulness practices within other and new activities in their daily interactions.

This continuous process of training, reflection and integration in daily live will be supported by using the journaling module of the app, with daily journaling guided by randomly selected positively formulated mindfulness-based questions (morning, afternoon and evening), aimed at practicing gratitude and optimism related to (a) daily experiences (always) and (b) positive anticipation on upcoming shared activities and (c) recalling positive memories after completing an activity (during activity planning and after completing activities). This module encourages girls three times a day to actively report on the positive aspects of preparing the activities together with their dyad friend, to actively recall positive memories about the activity as well as aspects of the friendship/sharing and the mindfulness practices after completing an activity. They will be encouraged to share their positive thoughts and positive emotions within their daily journaling and daily interactions and conversations.

During the training sessions, girls will be invited to share their experiences about their cultivated adaptive awareness of together dwelling on negative emotions and the impact of their training practices on awareness of sharing and responding on positive affect. This process will be specifically supported by the using the mood tracker and calendar, facilitating girls to reflect on practicing mindfulness-based activities and their daily emotions.

Daily state mood monitoring possibilities (three times a day: morning, afternoon and evening) are Positive Affect (PA): Cheerful (high arousal), Content (low arousal), Happy (high arousal), Energetic (high arousal), Relaxed (low arousal) and Joyful (high arousal) and Negative Affect (NA): Worried (high arousal), Anxious (high arousal), Low/Depressed (low arousal), Insecure (low arousal), Irritated (high arousal), and Guilty (low arousal). Girls will be asked to report one PA and/or one NA on a 5-point scale, ranging from 0 (*not at all*) to 4 (*very much*). The PA and NA items were derived from work of Barrantes-Vidal and colleagues [65]. A monthly overview of the experienced moods and their intensity will be available within the Mood calendar. Girls will receive daily empathetically formulated prompts on pre-programmed moments (indicated by the girls themselves) for using the mood monitoring, journaling and diary function of the app and daily rewards (i.e. psychoeducation), offered at completing daily mood monitoring and journaling. This is embedded to boost engagement with the app on a daily basis. It is hypothesized that actively practicing these skills and reflecting on the impact on their emotions and thoughts will explicitly target repetitive negative, judgmental emotions

and thoughts in the interactions and communication of the participating girls. Girls will spend a total of no more than 15 minutes a day completing the mood tracker and diary.

The program's aim is to teach emotion regulation and mindfulness skills on *the dyadic level* that support resilience and the positive qualities of girls' dyadic friendships with the aim to prevent excessive co-rumination and (early onset of) internalizing symptoms (depression, anxiety).

Teaching-and-care-as-usual (TAU)

In the control condition, girls receive unchanged any regular care and regular education. No other classroom-based mindfulness interventions will be implemented during the intervention period of the cRCT.

5.2 Use of co-intervention (if applicable)

Not applicable.

5.3 Escape medication (if applicable)

Not applicable.

6. INVESTIGATIONAL PRODUCT

6.1 Name and description of investigational product(s)

Not applicable.

6.2 Summary of findings from non-clinical studies

Not applicable.

6.3 Summary of findings from clinical studies

Not applicable.

6.4 Summary of known and potential risks and benefits

Not applicable.

6.5 Description and justification of route of administration and dosage

Not applicable.

6.6 Dosages, dosage modifications and method of administration

Not applicable.

6.7 Preparation and labelling of Investigational Medicinal Product

Not applicable.

6.8 Drug accountability

Not applicable.

7. NON-INVESTIGATIONAL PRODUCT

7.1 Name and description of non-investigational product(s)

Not applicable.

7.2 Summary of findings from non-clinical studies

Not applicable.

7.3 Summary of findings from clinical studies

Not applicable.

7.4 Summary of known and potential risks and benefits

Not applicable.

7.5 Description and justification of route of administration and dosage

Not applicable.

7.6 Dosages, dosage modifications and method of administration

Not applicable.

7.7 Preparation and labelling of Non Investigational Medicinal Product

Not applicable.

7.8 Drug accountability

Not applicable.

8. METHODS

8.1 Study parameters/endpoints

8.1.1 Main study parameter/endpoint

All data will be collected online via Qualtrics.

Screening measure (girls) and T0, T1, T2, T3, T4, and 1year follow-up measures T5 (girls)

Self-reported co-rumination

The original co-rumination measure consisted of 27 items designed to measure the extent to which youth typically engage in co-rumination with same-sex friends (Rose, 2002). It addresses nine key content areas, including (a) frequently discussing problems, (b) discussing problems rather than doing other activities, (c) friend encouraging discussion of problems, (d) target child encouraging friend to discuss problems, (e) discussing repetitively the same problem, (f) speculating about cause of problems, (g) speculating about consequence of problems, (h) trying to understand parts of problems, and (i) focusing on negative affective

feelings. The items are designed to assess a more intense form of discussing problems, going beyond typical self-disclosure. For this study, 9 items (one for each content area) will be used to evaluate co-rumination as screening and at T0, T1, T2, T3, T4, and the 1-year follow-up at T5. This shorter version is referred to as the Co-rumination Questionnaire-Short (CRQ-Short). These items include: “We talk about problems that my friend or I are having almost every time we see each other”, “When we see each other, if one of us has a problem, we will talk about the problem even if we had planned to do something else together,” “When my friend has a problem, I always try really hard to keep my friend talking about it.,” “When I have a problem, my friend always tries to get me to tell every detail about what happened,” “When we talk about a problem that one of us has, we’ll talk about every part of the problem over and over,” “When we talk about a problem that one of us has, we talk about all of the reasons why the problem might have happened,” “When we talk about a problem that one of us has, we try to figure out every one of the bad things that might happen because of the problem,” “When we talk about a problem that one of us has, we spend a lot of time trying to figure out parts of the problem that we can’t *understand*,” and “When we talk about a problem that one of us has, we talk a lot about how bad the person with the problem feels.” Rose (2002) found that her 27-item co-rumination measure was unifactorial, and a factor analysis of the 9-item version used by Hankin et al. (2010) similarly identified a single factor. In the studied sample, the 9-item measure demonstrated strong internal consistency, with Cronbach’s alpha values of 0.89 at Time 1, 0.91 at Time 2, and 0.91 at Time 3. Girls will respond to the items using a 5-point Likert scale ranging from 0 (“not at all true”) to 4 (“really true”), with the overall score calculated as the mean of the nine items. Rose et al. (2007) reported excellent internal consistency, good test–retest reliability, and strong validity for the measure.

8.1.2 Secondary study parameters/endpoints

T0, T1, T2, T3, T4, and 1-year follow-up measures T5 (girls)

Self-reported depressive symptoms/disorder

The self-reported level of depressive symptoms will be assessed using the Child Depression Inventory 2 (CDI-2; Boddien, Braet, & Stikkelbroek, 2016), a 28-item questionnaire. Each item provides three response options, scored from 0 to 2 (e.g., 0 = “I am sad once in a while,” 1 = “I am sad many times,” and 2 = “I am sad all the time”), with respondents selecting the option that best describes their experience. Higher scores indicate greater depressive symptoms, with total scores ranging from 0 to 56. A score of 12 or higher is considered clinically relevant. The CDI-2 demonstrates strong internal consistency, test–retest reliability, and convergent validity

(Bodden, Braet, & Stikkelbroek, 2016). For the current study the item concerning suicide has been left out, resulting in a 27-item questionnaire.

Self-reported generalized anxiety symptoms/disorder

Self-reported generalized anxiety disorder will be assessed using the Dutch version of the Generalized Anxiety Disorder (GAD) subscale from the Revised Children's Anxiety and Depression Scale (RCADS) (Chorpita et al., 2000). This subscale consists of six items (e.g., "I worry about things") and evaluates generalized anxiety on a 4-point scale (0 = never, 3 = always). The RCADS is known for its strong psychometric properties, demonstrating excellent reliability and validity (Chorpita et al., 2000; Chorpita, Moffitt & Gray, 2005). The official Dutch translation of the RCADS, which is available for free, will be used. Previous studies have shown that the Dutch version of the Generalized Anxiety Disorder (GAD) subscale has good internal consistency, validity, and sensitivity to change (Kösters et al., 2015).

Self-reported positive and negative affect

Self-reported positive and negative affect will be assessed using the Dutch version of the Positive and Negative Affect Schedule for Children (PANAS-C; Laurent et al., 1999; De Bolle, De Fruyt & Decuyper, 2010). The PANAS-C includes two subscales: Positive Affect (15 items, e.g., energetic) and Negative Affect (15 items, e.g., nervous). Participants will be asked to indicate how often they have experienced each feeling over the past few weeks, using a scale from 1 (very slightly or not at all) to 5 (extremely). The internal reliability of the Dutch version was found to be moderate to good, with Cronbach's α ranging from 0.66 to 0.83 for the Positive Affect subscale and 0.67 to 0.81 for the Negative Affect subscale. Additionally, a dummy variable will be created to represent the type of day (0 = weekend, 1 = weekday). To account for the time of day, separate dummy variables will be created to indicate whether the assessment occurred in the morning (1 = morning, 0 = afternoon and evening), afternoon (1 = afternoon, 0 = morning and evening), or evening (1 = evening, 0 = morning and afternoon).

Self-reported interpersonal responses to positive affect

Self-reported interpersonal responses to positive affect will be measured using the Co-Dampening and Co-Enhancing Questionnaire (CoDEQ; Bastin, Nelis, Raes, & Bijttebier, 2018). The questionnaire consists of 18 items, with nine items measuring co-enhancing responses and nine items measuring co-dampening responses to positive feelings within dyads. Co-dampening responses describe reactions such as thinking about the fleeting nature of positivity, focusing on worries, emphasizing negative aspects of a positive event, making upward social comparisons (e.g., considering how others are better off), making external attributions (e.g., attributing success to luck), and reflecting on past negative events. In

contrast, co-enhancing items focus on positive reactions, including behavioral displays, focusing on positive feelings (e.g., thinking about how energetic one feels), thinking about positive past or future events, making downward social comparisons (e.g., comparing oneself to others who are less fortunate), and recognizing positive personal qualities (e.g., believing in one's ability to achieve goals). Respondents will indicate how often they respond in these ways when they or their friend feel happy and discuss it. The rating scale has four response options: almost never (1), sometimes (2), often (3), and almost always (4). The Cronbach's alphas for co-enhancing and co-dampening were 0.84 and 0.86, respectively.

Self-reported quality of the friendship with the dyad friend and investments in the interpersonal relation

Self-reported support quality of the friendship with the dyadic friend and investments in the interpersonal relationship will be measured using the Dutch version of the Network of Relationships Inventory (NRI; Furman & Buhrmester, 1992), which includes 36 items across seven subscales. The subscale Support consists of eight items. Girls and their best friend were instructed to take each other in mind while answering items such as: "How much does your best friend really care about you?". The subscale Relative Power consists of six items ("To what extent is your friend the boss in your relationship?"). The subscale Negative Interaction consists of six items ("Are you and your friend annoyed by each other's behavior?"). The subscale Seeks Safe Haven consists of three items ("To what extent do you visit your friend when you are upset?"). The subscale Provides Safe Haven consists of three items ("To what extent does your friend visit you when she is worried about something?"). The subscale Seeks Secure Base consists of three items ("To what extent does your friend support you in the things you do?"). Finally, the subscale Provides Secure Base consists of three items ("To what extent do you support your friend in the things she does?"). Responses will be rated on a 5-point Likert scale 0 (little or none) to 4 (the most). The English version of the NRI shows good psychometric properties in adolescent samples, such as high internal consistency and moderately high stability over a 1-year period (Furman & Buhrmester, 2009). Furthermore, in a Dutch sample that used a shorter version of the NRI friend-scales, it was shown that the internal consistencies were high for all variables (Cronbach's alpha range $\alpha = 0.82-0.93$) and that the factor and construct validity of the NRI are adequate (De Goede et al., 2009).

Self-reported self-worth

Self-reported self-worth will be measured with the original Dutch version of the Competentie-Beleving Schaal voor Kinderen (CBSK; Veerman, Straathof & Treffers, 1994) and is intended to measure self-worth in children between 8 and 12 years old. It assesses children's perceived competence and self-value, offering insights into their self-esteem and overall self-concept. It

consists of 36 items across six subscales (e.g., scholastic competence, social competence, athletic competence, physical appearance and behavioural conduct and global self-worth). The CBSK has been evaluated through the Commissie Testaangelegenheden Nederland (COTAN). On three criteria it scored good: test construction principles, quality of test materials, quality of the manual. The aspects of norms, reliability and construct validity are rated as sufficient. The aspect of criterion validity is rated as insufficient (Kraijer & Plas, 2006).

T0 and T4 measures (parents)

Parental health care use of their child/family

Parental health care use for their child/family will be assessed through three questions: (1) whether the child and/or family received health care for psychosocial, emotional, or behavioral problems in the past 12 months, (2) the underlying cause(s) of the care, and (3) the duration of the care received.

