2. OBJECTIVES

Primary Objective: The primary objective of the Girls United cluster Randomized Controlled Trial (cRCT) is to examine the effectiveness of the Girls United prevention program on self-reported co-rumination.

Secondary Objectives: The second objective of this study is to investigate the intended active mechanisms of this program, especially enhancement of mindfulness and emotion regulation skills. Furthermore, the effectiveness of the Girls United mindfulness-based prevention program on self-reported symptoms of depression and anxiety, self-reported contagion of depression and anxiety symptoms, self- and friend-reported friendship quality, self-reported positive and negative affect, interpersonal responses to positive affect, self-reported self-worth

and parent-reported health care use will be studied in Dutch young adolescent girls from age 10 to 12 years old.

The research question is: To what extent does the app-based mindfulness prevention program Happy Friends, Positive Minds impact mental health and well-being in Dutch 10-to-12-year-old girls?

Hypotheses:

- (1) Girls in the intervention group will have a greater reduction in co-rumination (primary outcome) about distress and difficult emotions and feelings, (and thereby) internalizing symptoms (depression/anxiety, secondary outcome) and negative affect (secondary outcomes) during the intervention period, immediately after the intervention period and after one-year follow-up, relative to girls in the control condition.
- (2) Girls in the intervention group will have less dyadic depression contagion, immediately after the intervention period and after one-year follow-up, relative to girls in the control condition.
- (3) Girls in the intervention group will demonstrate less dyadic anxiety contagion during the intervention period, immediately after the intervention period and after one-year follow-up, relative to girls in the control condition.
- (4) Girls in the intervention group will experience better friendship quality, higher levels of positive affect and higher levels of interpersonal responses to positive affect, during the intervention period, immediately after the intervention period and after one-year follow-up, relative to girls in the control condition.

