- (5) The hypothesized intervention effects on co-rumination will be mediated by the development of mindfulness and emotion regulation skills during the intervention period, immediately after the intervention period and after one-year follow-up.
- (6) Girls in the intervention group will experience greater feelings of self-worth and will show less health care use during the intervention period, immediately after the intervention period and after one-year follow-up, relative to girls in the control condition.

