- Access to a support contact within the program for concerns or guidance. - Signposting to appropriate professional support services as appropriate (e.g., school-based counsellors, external mental health resources) if additional intervention is required.

Participation in the CDI-2 measures at T0 to T5

The PI will inform parents or main caretakers by phone if the girls score above 12 on the CDI-2 (the cutoff score for possible depression). They will be advised to contact their family doctor or the independent Health Care Professional for further guidance.

Participation in the RCADS-measures at T0 to T5

The PI will inform parents or caretakers by phone if the girls have a T-score greater than 65 on the RCADS (the cutoff score for possible anxiety disorder). They will be advised to contact their family doctor or the independent Health Care Professional for further guidance.

Participation in the intervention condition

1. *Participating in the online training sessions*

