For the model where co-rumination is measured via self-report, a multi-level (LGM) model, with intervention arm as the exogenous predictor variable, growth rate of mindfulness and emotion regulation skills as the mediating variables and growth rate of co-rumination as the primary outcome variable. The mediator and primary and secondary outcome variables will be modelled on both the individual (within) level and on the dyadic (between) level. This way, the between-level intervention effects will be adjusted for variation between individuals in co-rumination (primary outcome), internalizing symptoms (depression/anxiety, secondary outcomes) and negative affect (secondary outcome) on the within-level. Note that we have no a priori hypotheses regarding the nature of the growth patterns of the mediator and outcome variables and that they may be best captured by either a linear or a non-linear slope. We will adjust the analysis accordingly.

Hypothesis 6 “Girls in the intervention group will experience greater feelings of self-worth and will show less health care use, immediately after the intervention period and after one-year follow-up, relative to girls in the control condition” will be tested using multi-level LGMs for each outcome, respectively.

Two multi-level LGMs with intervention arm as the exogenous predictor variable and growth rate self-worth and health care use as the (potentially correlated) outcome variables, will be used to test whether girls in the intervention arm experience more feelings of self-worth and less health care use over time, compared to girls in the control arm. The outcome variables will be modelled on both the individual (within) level and on the dyadic (between) level. This way, the between-level intervention effects will be adjusted for variation between individuals in the outcome measures on the within-level. Please note that health care use will be modelled as a categorical LGM due to the nature of the data (dichotomous). Furthermore, note also that we have no a priori hypotheses regarding the nature of the growth patterns of the outcome

measures and that it may best captured by either a linear or a non-linear slope. We will adjust the analysis accordingly.

Statistical software

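### The health-care-use item does not separate the girl's care from unrelated care of other family members, although Hypothesis 6 is about the girls

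*Protocol*

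**What the plan says.** **Target.** Protocol section 2 says that "parent-reported health care use will be studied in Dutch young adolescent girls". Hypothesis 6, in the same section, states that girls in the intervention group "will show less health care use during the intervention period, immediately after the intervention period and after one-year follow-up", relative to control girls. Section 10.2 repeats the target: "less health care use over time, compared to girls in the control arm". It models health care use as a categorical growth model because the variable is dichotomous.

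**Measure.** Section 8.1.2 has parents answer three questions at T0 and T4. The first asks "whether the child and/or family received health care for psychosocial, emotional, or behavioral problems in the past 12 months". The others are listed as "2) the underlying cause(s) of the care, and (3) the duration of the care received". No question asks who received the care.

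**Contact with parents.** Under section 9.2.2, the principal investigator phones parents when a girl exceeds the CDI-2 or RCADS cut-off at any of T0 to T5. Of these parents the section says: "They will be advised to contact their family doctor or the independent Health Care Professional for further guidance". Nothing limits this to one arm. Section 5.1 describes the comparator thus: "In the control condition, girls receive unchanged any regular care and regular education".

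**The concern.** The hypothesis is about one person and the item is about a household. If a parent or brother had psychosocial care and the girl had none, the item still reads yes. Such answers carry no information about the effect of the program on the girl. They raise the recorded proportion in both arms and shrink the difference between them.

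A later analysis plan can do little about this, because the recipient is not collected. The health-care half of Hypothesis 6 could then look null because of the item rather than the program.

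A smaller matter concerns the comparator. Parents in both arms may be told of a high score and advised to make contact with a professional. Section 5.1 nevertheless describes control-arm care as unchanged.

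**Working it through.** The protocol states no rate, effect size or sample size for health care use, so there is no figure of its own to reproduce. All rates below are assumptions.

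**1. Does the item match the target?** Section 2 and section 10.2 name the girls. Question 1 in 8.1.2 covers the child, the family or both. Questions 2 and 3 cover cause and duration. With a yes/no outcome, a girl's own care and a relative's unrelated care receive the same code.

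**2. Size of the dilution.** Let *p* be the proportion of girls with own care. Let *f* be the proportion with unrelated family care among girls without own care, taken as equal in both arms. Then

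- P(yes) = 1 − (1 − *p*)(1 − *f*)
- recorded difference = (1 − *f*) × true difference
- *z* = difference / √{[P_C(1 − P_C) + P_T(1 − P_T)] / *n*}
- sample-size factor for equal power = (*z* for own care / *z* for the item)²

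Inputs: *n* = 160 girls per arm (the maximum in section 8.2), dyad clustering ignored, own care 15% in control and 10% in intervention.

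| *f* | Item, control | Item, intervention | Difference | Risk ratio | Factor |
|---|---|---|---|---|---|
| 0 | 15.0% | 10.0% | 5.0 points | 0.67 | 1 |
| 10% | 23.5% | 19.0% | 4.5 points | 0.81 | 1.9 |
| 20% | 32.0% | 28.0% | 4.0 points | 0.88 | 3.0 |
| 30% | 40.5% | 37.0% | 3.5 points | 0.91 | 4.4 |

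Worked row, *f* = 20%:

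- Own care: *z* = 0.05 / √[(0.1275 + 0.0900)/160] = 1.36.
- Item: *z* = 0.04 / √[(0.2176 + 0.2016)/160] = 0.78.
- Factor: (1.36/0.78)² ≈ 3.0.

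Row *f* = 30%: (0.05²/0.2175) / (0.035²/0.4741) = 4.4.

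A larger assumed effect shows the same pattern. With own care 20% versus 10%, two-sided alpha 0.05 and 160 per arm, power is 0.71 for own care. It falls to 0.48, 0.33 and 0.25 for *f* of 10%, 20% and 30%.

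**3. Which calls can enter the outcome?** Section 3 places T0 and T4 in September 2025 and May 2026 for cohort 1 (8 months apart), and in February and December 2026 for cohort 2 (10 months apart). The 12-month look-back at T4 therefore covers the whole period from T0. Care that follows a call made after T0, T1, T2 or T3 can be reported at T4. Calls after T4 scores would generally come after the parent's T4 report. T5 calls cannot enter, since the item is not asked again.

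**The case against.** **Dilution is not invalidity.** A reader might infer that the item cannot show anything about the girls. The protocol does not support that. Unrelated family care falls on both arms alike under randomisation, so it reduces sensitivity and leaves the contrast valid.

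**Family care may be the girl's care.** Help for a child's emotional problems is sometimes given to the family as a unit, and the item may intend this. That stands, and the fix has to keep such care. The cause question might also let some answers be sorted afterwards, but the protocol states no rule for it. Section 8.1.2 describes the questions rather than printing the form, but nothing there suggests that the recipient is recorded.

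**The calls.** A reader might infer that the trial creates the events it counts, or that the outcome merely repeats the symptom scales. Neither follows. A call is advice to make contact, not care received, and uptake is unknown. T0 alerts precede the program and should balance in expectation. After that, less care through fewer symptoms is a legitimate program effect. What stands is narrower: care alongside parent notification is not quite unchanged care. In addition, section 9.2.2 gives the intervention arm further routes to such advice, through disclosures in sessions and in the app diary, so the number of prompts need not be equal.

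**Assumed rates.** The protocol supplies none, so the factors show scale only. In the 15% versus 10% case, own care alone gives *z* = 1.36 at full enrolment. Splitting the item removes the dilution but does not make that comparison well powered.

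**Conclusion.** The mismatch is real and plain in the text: the hypothesis and analysis concern the girl, while the item covers the child and/or family without identifying the recipient. The consequence is dilution toward no difference in one half of one secondary hypothesis.

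Its size cannot be derived from the protocol. Under the assumed 15% versus 10%, the sample needed for equal power grows about 1.9-, 3.0- and 4.4-fold at 10%, 20% and 30% unrelated family care. This rests on family care being independent of the girl's care and of arm, and on ignoring clustering. If unrelated family care is concentrated in households where the girl also has care, the dilution is smaller.

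The secondary point concerns description. The comparison is with usual care plus notification of parents after high scores, and it remains a valid randomised comparison on those terms.

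**What to change.** In section 8.1.2, split question 1 into two parts:

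- (a) care for the participating daughter, including family-level care given because of her problems;
- (b) care for other family members that is unrelated to her.

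Name (a) as the health-care outcome of Hypothesis 6 in section 10.2, and ask both parts at T0 and T4.

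In section 5.1, describe the control as teaching-and-care-as-usual plus symptom monitoring with notification of parents. Report the number of girls above the alert cut-offs by arm and wave. The CDI-2 and RCADS scores already collected give this. Keep it descriptive: dividing the outcome by whether a call prompted the care would condition on a post-randomisation event, judged by parents who know the allocation (section 8.2). The alert procedure itself needs no change for this purpose.

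The cost is one extra parent question and a few lines of text. The small downside is that the item is no longer identical to the family-level question. For parent forms already completed, the recipient would have to be asked again.
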